AE	Adverse Event/Adverse Experience
CFR	Code of Federal Regulations
CRF	Case Report Form
DSMB	Data and Safety Monitoring Board
FDA	Food and Drug Administration
GCP	Good Clinical Practice
HIPAA	Health Insurance Portability and Accountability Act
IB	Investigator's Brochure
IND	Investigational New Drug Application
IRB	Institutional Review Board
PHI	Protected Health Information
PI	Principal Investigator
SAE	Serious Adverse Event/Serious Adverse Experience
SOP	Standard Operating Procedure

Study Summary

Title	EXPAREL transversus abdominis plane block vs. intrathecal analgesia in colorectal surgery: a prospective randomized trial.
Running Title	EXPAREL injection vs. intrathecal analgesia
Protocol Number	14-003143
Phase	Phase IV
Methodology	Prospective, randomized trial
Overall Study Duration	12 months
Subject Participation Duration	2-5 days
Single or Multi-Site	Single institution, multicenter
Objectives	Compare postoperative pain control between intrathecal analgesia and EXPAREL transversus abdominis plane injection. Length of stay, and complications will also be recorded.
Number of Subjects	226 total for both sites
Diagnosis and Main Inclusion Criteria	Consentable, nonpregnant adults undergoing elective colorectal surgery and enrolment in enhanced recovery program
Study Product, Dose, Route, Regimen	Liposomal injectable bupivacaine, injected once in the transversus abdominis plane bilaterally, 133mg per side.
Duration of Administration	Once
Reference therapy	Intrathecal hydromorphone
Statistical Methodology	Patients will be randomized in a 1:1 fashion. There will be two stratification factors: MIS vs. open surgery, and site (Jacksonville vs Rochester). Randomization will be performed with an online system and will use a permuted block design with varying block sizes

1 Introduction

This document is a protocol for a human research study. This study will be carried out in accordance with the applicable United States government regulations and Mayo Clinic research policies and procedures.

1.1 Background

Multimodal analgesia has played a key role in decreasing postoperative pain in patients undergoing colorectal operations. Recently, its role in decreasing oral morphine equivalents (OME) has been shown to decrease length of stay (LOS) and decrease the risk of postoperative ileus (POI) at Mayo ¹. Multimodal analgesia and limiting systemic opiate use are critical components in enhanced recovery pathways. Numerous studies have assessed the best agent and mode of neuraxial blockade. Its role in decreasing narcotic use and improving POI and LOS has been well-studied ²⁻⁴. Currently at our institution, single injection intrathecal hydromorphone analgesia is routinely used in addition to systemic, non-opiate analgesia (e.g., gabapentin, acetaminophen, non-steroidal anti-inflammatory medications).

Transversus abdominis plane (TAP) block is an alternative to neuraxial analgesia, and it has had promising results for analgesia after colorectal surgery ⁴⁻⁶. A limitation of bupivacaine TAP blockade is the relatively short duration of effect, ranging on average from 6-12 hours ⁷. Liposomal bupivacaine (EXPAREL) is a relatively new product currently FDA-approved for wound infiltration with an analgesic effect for 72 hours. EXPAREL has been shown to be safe and effective.

1.2 Investigational Agent

EXPAREL has been approved by FDA in 2011, and has been used for wound infiltration and nerve blocks. Its analgesic effects can last up to 72 hours. It is encapsulated in vesicular liposomes, which dissolve slowly, and release bupivacaine over time, providing a longer analgesic effect than ordinary bupivacaine ^{8,9}. EXPAREL is supplied in one vial, containing 266mg of bupivacaine suspended in multivesicular liposomes in normal saline. (DepoFoam) ¹⁰.

1.3 Clinical Data to Date

FDA approval was based on two double blind, Phase III trials on soft tissue and orthopedic surgical models. Subsequent to that, the medication was used in another Phase III trial with patients having bunionsectomies ¹¹. It found that EXPAREL use in 97 patients was associated with better postoperative pain, and no adverse side effects were found. Subsequently, another randomized, double blind, prospective Phase III trial was done, in patients undergoing hemorrhoidectomy ¹². The EXPAREL group (n=94) had less pain, and used less opioid medication. No adverse events were observed.

The safety profile of EXPAREL has been evaluated and in a meta-analysis, and its side effect profile has been found to be similar to bupivacaine. The most common side effects in the 800 patients in the EXPAREL group were nausea (3.3%) and constipation (2.0%). Cardiac complications were tachycardia (4%), and bradycardia (2%), which did not require treatment, and were similar to bupivacaine group. One death was reported in the 800 patients that received EXPAREL, and one in the bupivacaine group; both drugs were deemed as not the causative agents ¹³.

EXPAREL has been used in TAP infiltrations and has been used in two small studies totaling 37 patients. No side effects were reported, and the patients had low pain scores, with minimal narcotic use ^{14,15}.

At our institution, EXPAREL has been used for over one year with hundreds of patients both in the Rochester and Jacksonville campuses without any side effects attributed to EXPAREL injection.

1.4 Dose Rationale and Risk/Benefits

After induction of anesthesia, the patients will receive a single injection with 133 mg of EXPAREL suspended in 20mL of injectable saline, in each side, in the transversus abdominis plane (TAP). The injection will be ultrasound guided, and performed by our interventional anesthesiologists. The risks are the same as any non-EXPAREL TAP block, which include bleeding, infection, and pain. Systemic absorption of EXPAREL is possible, but as above (section 1.3), the side effects have not been found to be any different than the use of ordinary bupivacaine.

The risks will be included in the consent form, which include arrhythmias, bleeding infection, pain, and are no different than the use of TAP Bupivacaine, which is a standard of practice in our institution.

The alternate treatment group (the control group) will receive 100 mcg hydromorphone in a single intrathecal injection, administered by our interventional anesthesiologists immediately preoperatively. This is currently used routinely in the colorectal practice, as well as other practices across the enterprise.

2 Study Objectives

Primary Objective

To assess efficacy of EXPAREL TAP blocks in improving pain scores for 48 hours postoperatively, and in reducing total oral morphine equivalents (OME) use, compared to standard Intrathecal opioid administration (IT).

[figure not shown]
Secondary Objective

Assess the length of stay (LOS), postoperative ileus (POI) incidence, and the use of intravenous patient controlled analgesia (PCA) in patients that had EXPAREL TAP blocs compared to IT.

3 Study Design

3.1 General Design

This study is prospective, randomized trial in which EXPAREL TAP block is compared to standard IT opioid administration, in relieving postoperative pain, decreasing length of stay, and use of narcotic medication. Subjects will be screened at outpatient clinic visit appointments and interested qualified subjects will be consented and offered participation in this trial. All enrolled patients will be entered by the surgeon through written informed consent. All data will be entered in a prospective automated institutional database.

3.2 Primary Study Endpoints

Primary end points include mean pain scores for 48 hours and OME use associated with IT and EXPAREL TAP.

3.3 Secondary Study Endpoints

Secondary endpoints include LOS, the incidence of POI, and use of PCA

3.4 Primary Safety Endpoints

Patients will be monitored both intraoperatively and postoperatively for any adverse events (as defined below and in section 8). Patients will be connected to a cardiac monitor intraoperatively, and until the morning of postoperative day 1 (POD1). Patient will also be connected to a continuous pulse oximeter until the morning of postoperative day 1 (POD 1). These are standard practice for the recovery units. The surgical team will assess the patient routinely twice daily, more often if necessary. Vital signs (heart rate, oxygen saturation, and blood pressure) will be captured at least four times per day, more frequently if the clinical situation dictates. In addition, patients will all have a complete blood count, and creatinine checked on POD1 routinely. None of the patients enrolled in the trial will receive any amide-type anesthetics within 72 hours after EXPAREL use.

4 Subject Selection Enrollment and Withdrawal

4.1 Inclusion Criteria

- All patients undergoing elective minimally invasive or open small bowel or colorectal resections who are eligible for IT, and able to be enrolled in ERP.
- Age >18 years
- BMI <40
- Ability to understand and read English

4.2 Exclusion Criteria

- Not able or unwilling to sign consent.
- Currently pregnant or lactating.
- Patients with chronic pain, requiring daily opiate use at time of surgery.
- Patients intolerant or allergic to opiates, NSAIDS, acetaminophen or amide-type local anesthetics.
- Patients requiring emergent surgery.
- Abdominoperineal resections.
- **Any contraindications to neuraxial analgesia (coagulopathy, localized infection at the potential site of injection, pre-existing spinal canal pathology, previous spine surgery or peripheral neuropathy)**
- Patients with a diagnosis of inflammatory bowel disease.

- Patients have had or planned to have hepatic resection
- AST and/or ALT abnormal
- Renal insufficiency (creatinine clearance less than 30)
- Any patient currently receiving any anticoagulation medication other than aspirin, and/or with an INR > 1.4, as per ASRA guidelines ¹⁶.

4.3 Subject Recruitment, Enrollment and Screening

After institutional review board approval, all adult patients undergoing elective laparoscopic and open colorectal resections are considered for admittance into the trial. All enrolled patients will be entered by the surgeon through written informed consent. All patients enrolled will need to meet the inclusion idea (see section 4.1).

4.4 Subjects

4.4.1 When and How to Withdraw Subjects

Patients may withdraw from the study at any point before induction of anesthesia for their elective operation.

4.4.2 Data Collection and Follow-up for Withdrawn Subjects

Patients that withdraw from the study will not have received the treatment; therefore, no data will need to be collected, other than that they were considered for enrolment.

5 Study Drug

5.1 Description

The EXPAREL solution will be housed in a transparent vial, which will appear milky-white because the solution itself is milky white.

5.2 Treatment Regimen

After induction of anesthesia, the patients will receive a single injection with 133 mg of EXPAREL in the transversus abdominis plane (TAP), on each side, suspended in 20mL of injectable saline.

5.3 Method for Assigning Subjects to Treatment Groups

All enrolled patients will be entered by the surgeon through written informed consent. Patients will be randomized 1:1 to either receive:

Group A: IT

Or

Group B: EXPAREL TAP.

There will be two stratification factors: type of surgery (MIS versus open), and site (Jacksonville versus Rochester).

5.4 Preparation and Administration of Study Drug

EXPAREL is suspended in 20 ml of injectable saline from the manufacturer (containing 266 mg of liposomal bupivacaine). An additional 20 mL of injectable saline will be used to

further dilute the drug to a total volume of 40ml. Under ultrasound guidance, 20 ml (133 mg) of the solution will be injected once in the transversus abdominis plane on each side. Thus, each side will receive 133 mg of EXPAREL suspended in 20 mL of saline.

5.5 Subject Compliance Monitoring

Patients receiving treatment will be enrolled in a prospective database. No other treatment is necessary, except the single injection before their scheduled procedure.

5.6 Prior and Concomitant Therapy

Patients may receive therapy for any conceivable condition, while enrolled in this trial, as long as they meet the inclusion criteria (section 4.1).

5.7 Packaging

Exparel solution will be packaged from the manufacturer, and will appear as a vial containing 20 ml of milky white suspension.

5.8 Masking/Blinding of Study

The study will not be blinded.

5.9 Receiving, Storage, Dispensing and Return

5.9.1 Receipt of Drug Supplies

EXPAREL is already being used throughout the enterprise, and its storage, handling, transport and disposal will not change.

5.9.2 Storage

EXPAREL is already being used throughout the enterprise, and its storage, handling, transport and disposal will not change.

5.9.3 Dispensing of Study Drug

EXPAREL is already being used throughout the enterprise, and its storage, handling, transport and disposal will not change.

5.9.4 Return or Destruction of Study Drug

EXPAREL is already being used throughout the enterprise, and its storage, handling, transport and disposal will not change.

6 Study Procedures

EXPAREL is administered only once as described in section 5.4.

Safety data will be collected on the patient for 30 days, +/- 10 days after administration of study treatment. The collection of data will be through the patient's medical record from their normal post-operative care visits to the clinic. If the patient does not return to the clinic, they patient will be contacted by phone to assess the patient for any adverse events. All adverse events are reported to the study PI.

7 Statistical Plan

7.1 Randomization

Patients will be randomized in a 1:1 fashion. There will be two stratification factors: type of surgery (MIS vs. open surgery) and site (Jacksonville versus Rochester). Randomization will be performed with an online system and will use dynamic allocation..

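### The Study Summary and section 7.1 name different randomisation methods, and under either one the primary t-test leaves out the stratification factors

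*Combined protocol and SAP*

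**What the plan says.** The Statistical Methodology row of the Study Summary reads: "Randomization will be performed with an online system and will use a permuted block design with varying block sizes". Section 7.1 starts its sentence the same way and ends it differently: "Randomization will be performed with an online system and will use dynamic allocation". The two places agree on the rest, namely 1:1 allocation stratified by surgery type (MIS or open) and site (Jacksonville or Rochester). Section 5.3 repeats the ratio and the factors but names no algorithm.

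Section 5.8 states: "The study will not be blinded". Section 4.3 states: "All enrolled patients will be entered by the surgeon through written informed consent".

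Section 7.3 compares mean pain AUC with a two-sample t-test. It compares 48-hour OME with a two-sample test, on the log scale or by Wilcoxon rank sum if the data are skewed. Neither primary comparison includes the stratification factors. Linear regression is a secondary analysis, used only for baseline variables found to be imbalanced.

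**The concern.** One online system can be set up in only one of these ways, so one of the two statements is wrong. A monitor could not confirm that the system follows the protocol, because either setting departs from one of the texts. A publication could not describe the method reliably either.

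The choice matters because the trial is open label and surgeons enter the patients. Whoever can guess the next arm can influence which patient is entered next, and that can bias any endpoint. How guessable the sequence is depends on the details that are missing.

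A second issue comes from the same section of the plan. Both methods balance the arms on site and approach. An analysis that ignores balanced factors counts their variation as noise, although the design has largely removed it from the treatment comparison. The standard error is then overstated.

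**Working it through.** **1. Side-by-side reading.** The ratio, the factors and the online system are the same in the Study Summary and section 7.1. Only the algorithm differs. Section 5.3 cannot break the tie, and there is no precedence rule or amendment log that marks either text as superseded. Both sentences are complete, so extraction from PDF does not explain the conflict.

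**2. The plan's own figures.** The documents give no figure for randomisation. The sample size in section 7.2 reproduces: n per arm = 2(1.96 + 0.8416)² / 0.40² = 98.1, so 99 (99.1 by noncentral t), against 100 planned. With 100 per arm, power is 80.4% at 0.40 SD and 94.0% at 0.50 SD, matching the stated 80% and 94%. The randomisation method does not enter this calculation.

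**3. Predictability, by simulation.** From the documents: 226 patients, 1:1, two binary factors. Assumed: the splits on the factors, the block sizes, and dynamic allocation modelled as minimisation on the two factor margins. The guess is always the under-represented arm. The full-knowledge column uses site 70/30 and surgery type 60/40, with 4,000 trials per method; site 50/50 and approach 70/30 gave the same 86%, 74% and 68% where both were run. The own-site column uses site 50/50 and approach 70/30, 400 trials, and the best of three guessing rules.

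| Method | Knows all earlier assignments | Knows own site only |
|---|---|---|
| Simple randomisation | 50% | not run |
| Blocks 4/6/8 | 68% | 68% |
| Blocks 2/4/6 | 70% | 70% |
| Minimisation, p = 0.7 | 67% | 61% |
| Minimisation, p = 0.8 | 74% | 66% |
| Minimisation, p = 1.0 | 86% | 74% |

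The figures for blocks do not change because the strata lie within site. Under minimisation the other site's assignments also feed the decision, so knowing one site gives less. If a surgeon knew only his or her own patients (four surgeons per site assumed), every method gave about 52%.

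**4. The unadjusted t-test.** Assume effects of 1.0 SD for surgery type (60/40) and 0.5 SD for site (70/30), in units of the residual SD.

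- Outcome variance within an arm = 1 + 1.0² × 0.6 × 0.4 + 0.5² × 0.7 × 0.3 = 1 + 0.24 + 0.0525 = 1.2925.
- With both factors balanced, the treatment difference varies only with the residual variance of 1. The t-test's standard error is therefore too large by √1.2925 = 1.137, about 14%.
- Type I error ≈ 2 × [1 − Φ(1.971 × 1.137)] = 2 × [1 − Φ(2.240)] = 0.025.

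Simulation (4,000 runs, Monte Carlo SE about 0.0035) agrees:

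| Method | Unadjusted t-test | Both factors in model |
|---|---|---|
| Simple randomisation (3,000 runs) | 0.048 | 0.048 |
| Blocks (three sets of sizes) | 0.025 to 0.030 | 0.046 to 0.050 |
| Minimisation, p = 0.7 to 0.9 | 0.024 to 0.030 | 0.047 to 0.051 |
| Minimisation, p = 1.0 | 0.029 | 0.059 |

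If both effects are halved (0.5 and 0.25 SD), the variance is 1 + 0.06 + 0.0131 = 1.0731, the standard error is 3.6% too large, and the type I error is about 0.041. With no factor effect there is no error to correct.

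**The case against.** A reader might infer that dynamic allocation is the dangerous option, that the enrolling surgeon sees every assignment, and that blocks should therefore be preferred. The documents do not support this. They say that surgeons enter patients and that the trial is unblinded, not that any surgeon knows the whole sequence. There are two sites; section 8.6.1 refers to several participating surgeons; and section 9.2 has each campus record its data separately, with the data combined quarterly. The monthly meetings and by-arm reports (sections 8.5 and 8.6.1) concern adverse events. The 86% figure needs a deterministic algorithm, which the protocol never states. Minimisation at 0.7 is no more guessable than blocks even with full knowledge, and at 0.7 or 0.8 it is less guessable than blocks of 4/6/8 to someone who knows only one site.

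A reader might also infer that only dynamic allocation calls for adjustment, or that the planned test produces too many false positives. Neither follows. Stratified blocks raise the same issue to the same degree, and the error is conservative. Only deterministic minimisation behaves somewhat differently after adjustment (0.059). The methods do differ in the reference set for a randomisation-based test, but the plan proposes no such test.

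It could be said that the secondary regression already covers adjustment. It does not: it is triggered by imbalance, and the stratification factors are the variables least likely to be imbalanced.

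What stands of the objection is that the documents give no ground for ranking the two methods, and no evidence that any bias has occurred. The contradiction itself is untouched.

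**Conclusion.** The Study Summary and section 7.1 contradict each other on the randomisation method, and nothing in the protocol resolves it. That conclusion rests on the text alone. The consequence for predictability is undetermined. The 67% to 86% range is illustrative, assumes full knowledge of earlier assignments, and turns on block sizes or a random element that the plan does not state.

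Under either method the primary t-test omits the balancing factors. Its standard errors are too large to the extent that site or approach predicts outcome: about 14% with assumed effects of 1.0 and 0.5 SD (type I error about 0.02 to 0.03 instead of 0.05), and less with weaker effects. The price is precision and power, not false positives. The point should be corrected, but it does not invalidate the design or change the sample size.

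**What to change.** - Confirm how the online system was configured, and make the Study Summary and section 7.1 state that one method. The documents give no reason to favour either.
- If it is dynamic allocation, name the algorithm and specify a random element so that assignment is not deterministic.
- If it is permuted blocks, keep the block sizes out of any document that enrolling staff see.
- Under either method, include site and surgery type (MIS or open, as entered at randomisation) as covariates in the primary analyses of pain AUC and OME in section 7.3, for example in a linear model, with OME logged if skewed. If a rank test is kept as the fallback for OME, stratify it by the same factors.

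The cost is one check of a system setting and a few sentences in the protocol. Both factors are already recorded for stratification, so no extra data or patients are needed.

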7.2 Sample size

The two primary endpoints of interest are pain scores over 48 hours post-surgery and the amount of narcotic medication used, standardized to OME, over 48 hours post-surgery. The pain score endpoint will be summarized as area under the curve (AUC), normalized for the total time of observation. A sample size of 100 patients per arm provides 80% power to detect an effect size of 0.40 using a two group t-test with a 0.05 two-sided significance level. The effect size is the expected difference in the mean AUCs divided by the within group standard deviation. A difference of 0.5 standard deviations in pain scores has been demonstrated to be clinically meaningful in the QOL literature. This study is adequately powered to detect this; a sample size of 100 patients in each group has 94% power to detect a difference in the mean AUC pain scores between the two groups of 0.50 standard deviations. The narcotic medication use (standardized OME) will be the cumulative use over the 48 hour period. It is also felt that a difference of 0.4 standard deviations in the mean narcotic use (standardized to OME) between the groups is clinically meaningful.

7.3 Analysis plans

Patient Population(s) for Analysis

The patient for the primary analysis will be all randomized patients who did not withdraw prior to the initiation of anesthesia. The numbers of patients that withdraw prior to undergoing surgery will be monitored for imbalances between the arms.

Primary analysis plan

The primary analysis will be a modified intent-to-treat analysis. This means it will be an analysis of all randomized patients who did not withdraw prior to surgery according to the arm to which they were randomized.

The mean pain scores over 48 hours will be summarized as the area under the curve (AUC) of the observed pain score (y-axis) plotted by the time it was measured (x-axis). The difference in mean AUCs of the two groups will be evaluated using a two-sample t-test. In addition, the cumulative narcotic use over the 48 hour period will be determined for each patient (standardized OME). The difference in mean standardized OME will be compared with a two-sample test. If the data are skewed, a two-sample t-test will be performed on the logged values of OME or a Wilcoxon rank sum test will be used on the untransformed data. A two-sided p-value will be declared statistically significant for each primary endpoint. This will mean that the overall two-sided level of significance for the trial will be 0.10.

In addition to looking at the summary of the pain scores and OME scores, we will also plot these values over time and determine whether there are differences at individual time points.

Secondary analysis plan

The mean length of stay will be compared between the two groups with a two-sample test. If there are no outliers, a two-sample t-test will be used. If there are outliers, a Wilcoxon rank sum test will be used. A chi-square test (or Fisher's exact test) will be used to compare the rates of POI, need for a PCI and post-operative hypotension.

Comparisons will be made between the randomized groups of the baseline variables (patient, disease, and surgical) to determine if there were any randomization imbalances. If imbalances are found, a secondary analysis will be done using linear regression and adding the variables that were not balanced between the groups.

Descriptive Statistics

Univariable descriptive statistics will be calculated for all variables; categorical variables will be summarized as counts (relative frequencies) and continuous variables will be summarized as mean \pm standard (SD) and median (min value, max value).

Handling of Missing Data

Missing data will prompt individual review of the patient's electronic record to obtain missing variables. Analyses will be done using all patients who have the necessary data for the analysis. If the amount of missing data within an analysis is greater than 10%, imputation methods will be used and the data re-analyzed as a sensitivity analysis.

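### Both primary tests leave out the two stratification factors, so they run conservatively and give up some power if surgery type or site predicts outcome

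*Combined protocol and SAP*

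**What the plan says.** The Study Summary and sections 5.3 and 7.1 all name the same two stratification factors, surgery type (MIS or open) and site (Jacksonville or Rochester).

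Section 7.3 sets out the primary tests without them. For pain AUC: "The difference in mean AUCs of the two groups will be evaluated using a two-sample t-test". For narcotic use: "The difference in mean standardized OME will be compared with a two-sample test". If OME is skewed, the plan allows either a t-test on logged values or the rank alternative: "a Wilcoxon rank sum test will be used on the untransformed data".

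The only covariate adjustment is secondary and conditional: "If imbalances are found, a secondary analysis will be done using linear regression and adding the variables that were not balanced between the groups". No threshold for imbalance is given.

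Section 7.2 sizes the trial for the unadjusted test: "A sample size of 100 patients per arm provides 80% power to detect an effect size of 0.40 using a two group t-test", at a two-sided 0.05 level. It also states 94% power at 0.50 SD. The effect is scaled by the within-group standard deviation.

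**The concern.** Stratified allocation makes the arms alike on surgery type and site, so variation due to those factors largely cancels from the difference between arms. A plain t-test or rank sum test does not know this. It still counts that variation as noise, so its standard error is too large for the design. The test then rejects less often than its nominal 0.05 under the null, and less often than it could when there is a real effect.

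The imbalance-triggered regression does not repair this. It adds variables found to be unbalanced, and allocation is built to keep these two balanced. The factors the trial chose to control in the design are therefore the ones least likely to enter any analysis. The covariates in that regression would also be chosen after the data are seen.

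**Working it through.** **Inputs from the documents.** Allocation 1:1 (7.1); n = 100 per arm, two-sided 0.05, d = 0.40 and 0.50 within-group SD (7.2); unadjusted primary tests (7.3). **Assumed:** R², the share of within-arm outcome variance explained by the two factors. The documents give no value, so 0, 0.05, 0.10 and 0.20 are shown.

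**Step 1: the plan's own figures.** The noncentral t distribution with 198 degrees of freedom and noncentrality d√(n/2) gives 80.4% at d = 0.40 and 94.0% at d = 0.50. The stated 80% and 94% reproduce. The normal approximation used below gives 80.7% and 94.2%.

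**Step 2: the unadjusted test when the strata predict outcome.** With strata balanced across arms, the true variance of the difference in means is (2/n)σ²(1 − R²), but the t-test estimates (2/n)σ². Hence

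- true type I error = 2[1 − Φ(1.96/√(1 − R²))]
- unadjusted power = Φ[(d√(n/2) − 1.96)/√(1 − R²)]
- adjusted power = Φ[d√(n/2)/√(1 − R²) − 1.96]

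For d = 0.40, d√(n/2) = 0.40 × √50 = 2.828. At R² = 0.20, √(1 − R²) = 0.894. Type I error is 2[1 − Φ(2.191)] = 0.028, unadjusted power is Φ(0.868/0.894) = 83.4%, and adjusted power is Φ(3.162 − 1.96) = 88.5%.

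| R² | Type I error, unadjusted | Power at 0.40 SD, unadjusted | Power at 0.40 SD, adjusted | Gap (points) | n per arm for 80%, adjusted | Gap at 0.50 SD (points) |
|---|---|---|---|---|---|---|
| 0 | 0.050 | 80.7% | 80.7% | 0 | 99 | 0 |
| 0.05 | 0.044 | 81.4% | 82.7% | 1.3 | 94 | 0.5 |
| 0.10 | 0.039 | 82.0% | 84.7% | 2.7 | 89 | 1.0 |
| 0.20 | 0.028 | 83.4% | 88.5% | 5.1 | 79 | 1.6 |

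**Step 3: simulation for AUC.** In 20,000 trials per setting, with four equal strata balanced by arm and R² split equally over the two factors, t-test power at 0.40 SD was 80.1, 81.2, 81.7 and 82.6% for the four R² values. A linear model with arm and both factors gave 80.1, 82.5, 84.7 and 88.1%. Its type I error stayed at 0.047 to 0.053.

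**Step 4: rank test for OME.** Ranks do not change when values are exponentiated, so the same simulation covers lognormal OME. At 0.40 SD on the log scale, Wilcoxon power was 78.3, 79.4, 79.7 and 80.4%. Van Elteren power was 77.6, 80.1, 81.7 and 86.1%, a change of −0.7, +0.7, +2.0 and +5.7 points.

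**Step 5: allocation method.** The documents describe both permuted blocks and dynamic allocation, so both were simulated with 5,000 trials per setting and factor prevalences of 35% and 40% (assumed). At R² = 0.20 under blocks, type I error was 0.031 for the t-test and 0.051 for the adjusted model, and power was 82.4% against 87.8%. Under minimisation the figures were 0.030 and 0.048, and 82.9% against 88.1%. The finding is the same under either method.

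**Step 6: the imbalance rule.** Further assumptions are 226 randomised, 26 lost at random, surgery type split 60/40, site split 70/30, and imbalance defined as chi-square p < 0.05. Neither factor was flagged in any of 32,000 simulated trials.

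**The case against.** The strongest reply is that nothing in the plan fails. Section 7.2 powers a two-group t-test and section 7.3 uses one. The unadjusted test keeps at least the stated power at every R², and its type I error is never inflated. The loss exists only against an alternative that the plan did not promise. This is right, and it limits the severity.

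The size also depends on an undocumented R². With two evenly split factors sharing R² = 0.20, each must shift the outcome by 2√0.10 = 0.63 SD, more than the treatment effect sought. At R² = 0.05 the shift is still 2√0.025 = 0.32 SD. At 0.50 SD, the difference section 7.2 supports as meaningful for pain, the gap is under 2 points throughout. These points stand too. The top of the range should not be read as the expected case. The 0.40 SD case remains relevant, because section 7.2 sizes the trial on it and calls it meaningful for OME.

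The result on the imbalance rule rests on an assumed p-value trigger. That is true, but any sensible trigger would seldom select factors that allocation keeps balanced. Finally, the regression on unbalanced variables might be kept for non-stratified covariates. But its covariates are picked after the data are seen, and a set fixed in advance is the sounder choice.

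**Conclusion.** The concern holds as a matter of efficiency and prespecification. The primary tests omit the factors used in randomisation and will be conservative to whatever extent those factors predict pain or narcotic use. For R² from 0.05 to 0.20, the power forgone at 0.40 SD is about 1 to 5 points. At the upper end the chance of missing a real effect falls from 16.6% to 11.5% with no added patients. If R² is 0, the loss is nil. The calculation assumes additive stratum effects and allocation that balances the factors across arms. It does not call the sample size or the validity of the tests into question. The change should be made because it is nearly free, not because the trial would otherwise fail.

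**What to change.** In section 7.3, make the primary analysis of pain AUC a linear model with terms for arm, surgery type as recorded at randomisation, and site, testing the arm coefficient at two-sided 0.05. Use the same model for OME, on the log scale if skewed. Where the plan would use a Wilcoxon test, use a van Elteren test over the four surgery-type-by-site strata. Let this fixed covariate set replace the rule that adjusts for whatever proves unbalanced.

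The cost is wording only, since both factors are already recorded at randomisation. The linear model uses 2 extra degrees of freedom of about 198, with no measurable loss of power if the strata do not matter. The van Elteren test costs about 0.7 points of power in that case. This change does not settle the plan's open choice between logged and rank analysis of OME.

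A separate drafting point does not affect the result. The Study Summary describes permuted blocks of varying size, while section 7.1 says "Randomization will be performed with an online system and will use dynamic allocation". Both should state the one method actually used.
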